3.6 FEASIBILITY OF RECRUITMENT

The collaborative departments (Surgical Department and Gastroenterology department) of Royal Preston Hospital and the respective departments from Furness General Hospital screen approximately 18-20 cases per week. Assuming a participation rate of 50%, 500 patients can be recruited during a 12 months' period.

4. STATISTICAL ANALYSIS

4.1 Confirmatory analysis of primary endpoints

In order to compare the low to high risk groups, the propensity score will be used that is the probability of a case being in a particular group based on a given set of covariates (e.g., age, gender, BMI and ethnic background). Generally, will be calculated using logistic regression with group (Treatment /Control) as dependent and covariates as independent variables. In order to deal with missing data in covariates, we will apply multiple imputation by either Separate creation of propensity scores from the matching or we will aggregate cases to get mean (median) propensity score. H0: p1=p2 is tested against the alternative H1: $p1 \neq p2$ using the exact Fisher tests.

A receiver operating characteristic (ROC) curve will be used to summarize the performance of the two-class classifiers (for Neurotensin and IL-8) for cancer and adenomas across the range of possible thresholds.

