3.1 CONTROL(S) / COMPARATOR(S)

All individuals fulfilling the inclusion criteria will be enrolled. After the refinement of participants by the exclusion criteria blood sample will be drawn for Neurotensin and IL-8. Following the report of colonoscopy and the histology individuals will be assigned in three groups: a) group A - cancer patients, b) group B – adenoma (polyp) patients and c) group C – No pathology/normal colonoscopy. Two primary analyses will be conducted to define the cut-off plasma values for Neurotensin and IL-8 for a) diagnosing cancer (group A versus group C) and b) diagnosing adenomas (group B versus group C). A secondary analysis will be conducted comparing the performance of the Neurotensin/IL-8 system towards the 2-weeks referral and FOB test positive patients for the diagnosis of colorectal cancer and adenomas.

The reason for using participants without bowel pathology is because we need to define the "normal range" of Neurotensin and IL-8 serum values.

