3.3 OUTCOME MEASURES

The primary endpoints are firstly the cut-off of the serum Neurotensin and IL-8 values selected by the ROC curves and the demonstrated estimate of area under ROC curve (accuracy) in predicting colorectal cancer and colorectal adenomas.

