3.5 PROPOSED SAMPLE SIZE / POWER CALCULATIONS

Assuming that the AUC of the new test is commensurate with the pilot study (AUC=0.85), we calculate the number of samples required to obtain a 95%

confidence interval of size 0.1. We assume that the ROC curve follows a binormal distribution, and that the prevalence of adenoma/cancer is between 20-30% in the study participants. We obtain that we require between 400 (30% prevalence) and 553 (20% prevalence) participants. We therefore target an enrollment of 500 patients. We intend to perform an interim analysis after 50% of the patients have been included and evaluated.

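### The confirmatory test in section 4.1 compares two undefined proportions and does not address the ROC cut-offs and AUC that are the primary endpoints and the basis of the sample size

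*Protocol*

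**What the plan says.** Three parts of the protocol agree with one another.

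- Section 3.3 sets the endpoints: "the cut-off of the serum Neurotensin and IL-8 values selected by the ROC curves and the demonstrated estimate of area under ROC curve", for colorectal cancer and for adenomas.
- Section 3.1 sets the contrasts, cancer (A) versus normal (C) and adenoma (B) versus normal (C): "Two primary analyses will be conducted to define the cut-off plasma values for Neurotensin and IL-8".
- Section 3.5 sets the size: "Assuming that the AUC of the new test is commensurate with the pilot study (AUC=0.85"), for a 95% confidence interval of total width 0.1, with 20% to 30% of participants having adenoma or cancer. It gives 553 to 400 participants and a target of 500.

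Section 4.1, headed as the confirmatory analysis of the primary endpoints, opens differently: "In order to compare the low to high risk groups, the propensity score will be used". The score comes from "logistic regression with group (Treatment /Control) as dependent and covariates as independent variables". The hypothesis follows: "H0: p1=p2 is tested against the alternative" of inequality, by Fisher's exact test. A ROC curve is then planned to describe each marker's performance.

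Section 4.2 uses the same p1=p2 hypothesis for adenoma frequency and other qualitative characteristics. Section 4.5 plans an interim analysis of the primary endpoint at 250 persons and stops the study if H0 is rejected.

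**The concern.** A confirmatory analysis should test, or estimate against a stated criterion, the quantity named as the endpoint. Here the only stated hypothesis concerns two proportions that are not defined, between risk groups that are not groups A, B and C. Its propensity model uses treatment/control labels in a study without treatment. Rejecting equality of two proportions shows that they differ. It does not show that the AUC is near 0.85, or that any cut-off discriminates usefully.

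The point has a consequence because section 4.5 attaches a stopping decision to H0. On the only H0 in the document, the study could stop at half its sample on a test unrelated to AUC precision.

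**Working it through.** **1. The plan's own sample size.** Inputs from section 3.5: AUC 0.85, half-width 0.05, binormal ROC, prevalence 30% and 20%. Binormal (Obuchowski) variance, with a = 1.414·z(AUC) = 1.4655 and k = (1−prev)/prev:

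V = 0.0099·exp(−a²/2)·[(5a²+8) + (a²+8)/k]; cases = 1.96²·V/0.05²; N = cases/prev.

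- 30%: k = 2.333, V = 0.0781, cases = 120.0, N = 400.
- 20%: k = 4, V = 0.0720, cases = 110.6, N = 553.

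Both stated figures reproduce. The sample size is an AUC-precision calculation and uses no p1 or p2.

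**2. The sections side by side.**

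| | Sections 3.1, 3.3, 3.5 | Section 4.1 |
|---|---|---|
| Groups | A vs C, B vs C | low vs high risk, undefined; treatment/control |
| Quantity | cut-offs, AUC | p1, p2, undefined |
| Criterion | AUC interval width 0.1 | p1 ≠ p2 by Fisher; none for the AUC |

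**3. What rejecting p1=p2 could mean.** The protocol does not give these inputs, so they are assumptions: two-sided alpha 0.05; p1 and p2 are marker-positive rates in diseased and non-diseased; equal-variance binormal marker; fixed cut-off with 20% false positives. Group sizes: 25% prevalence (the middle of 20% to 30%) of 500 gives 125 vs 375, and of 250 about 62 vs 188. The 4% cancer pick-up rate in section 1.8 gives 20 cancers in 500, set against 375 normals.

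Sensitivity = Φ(√2·z(AUC) + z(0.20)). For AUC 0.65: Φ(0.545 − 0.842) = 38%. For AUC 0.60: Φ(0.358 − 0.842) = 31%.

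Exact probability that Fisher's test rejects:

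| True AUC | 125 vs 375 (pooled neoplasia) | 62 vs 188 (interim) | 20 vs 375 (cancer) |
|---|---|---|---|
| 0.65 | 97% | 79% | 44% |
| 0.60 | 71% | 43% | 22% |

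One observed split: 36/125 (28.8%) vs 75/375 (20%) gives p = 0.047, and the matching binormal AUC is Φ((z(0.288)+z(0.80))/√2) = 0.58.

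A different cut-off (sensitivity = specificity) at N = 500 and 20% / 30% prevalence gives 97% / 99% for AUC 0.65 and 70% / 81% for AUC 0.60. The pooled result does not hinge on the 20% false-positive rate.

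Stopping at 62 vs 188 also loses precision. With the step 1 variance at AUC 0.85, the half-width is 1.96·0.0347 = 0.068 (total width 0.136) against the planned 0.05.

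**4. Would an AUC criterion do better?** Rule: estimate − 1.96·SE must exceed a minimum AUC0. With the step 1 variance, find the smallest passing estimate t. The pass probability is Φ((AUC − t)/SE).

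| AUC0 | t, 125 vs 375 | AUC 0.60 | AUC 0.65 | AUC 0.85 |
|---|---|---|---|---|
| 0.50 | 0.557 | 93% | >99.9% | >99.9% |
| 0.70 | 0.755 | <0.1% | <0.1% | >99.9% |
| 0.75 | 0.802 | <0.1% | <0.1% | 97% |

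The Hanley-McNeil variance gives 91% instead of 93% in the first row and 99% instead of 97% in the last. With 20 vs 375, a true AUC of 0.85 passes in only 71% (AUC0 = 0.70, t = 0.818, SE 0.0571) or 43% (AUC0 = 0.75, t = 0.860).

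**The case against.** A reader might infer that a nearly useless marker would be declared confirmed. The documents do not support that. No section says that rejecting p1=p2 confirms a marker. Section 4.1 also plans the ROC curve and section 3.3 names the AUC, so a poor AUC would be visible. Section 2 calls the study a pilot, section 3 says the results do not affect participants' care, and section 5.5 foresees a further multicentre study. The 97% also pools cancer and adenoma, which is not one of the two primary contrasts. With 20 cancers it is 44%.

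A reader might also infer that the propensity score serves no purpose, or that Fisher's test must ignore it. That goes too far. Section 3.4 plans controls matched on gender, age, BMI and ethnic background, the covariates that section 4.1 lists. The score may be meant for case/control matching, and a test run on a matched sample uses the score through selection. The treatment label may be template wording.

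A separate analysis plan might define p1 and p2. But the protocol has already stated a test: a plan that followed it would carry the mismatch forward, and one that replaced it would contradict the protocol.

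These objections limit the size of the consequence. They leave standing the mismatch between endpoint and test, and the stopping rule attached to it.

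**Conclusion.** The point holds in this form: section 4.1 states a confirmatory test that does not address the primary endpoint or match the sample-size basis, and section 4.5 lets the only written H0 stop the study. This follows from the text and needs no assumption.

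The size does rest on assumptions (alpha, the meaning of p1 and p2, the cut-off, the group sizes). Under those stated, a marker with true AUC 0.65 rejects H0 in 44% to 97% of trials, and one with AUC 0.60 in 22% to 71%, depending on the contrast and the look. As written, rejection supports no conclusion about the AUC or a cut-off. The correction is cheap and should be made before the interim analysis.

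**What to change.** - **Section 4.1:** for each primary contrast (A vs C, B vs C), make the confirmatory result the AUC with its 95% confidence interval, and require the lower limit to exceed a minimum useful AUC fixed in advance and above 0.50. Changing the test while leaving 0.50 as the bar would not help. The values 0.70 and 0.75 are illustrations; the investigators must choose.
- **Section 4.5:** state that H0 is this same AUC hypothesis.
- **Fisher's test:** keep it for descriptive comparison of categorical characteristics.
- **Propensity text:** either reword it as the case/control matching of section 3.4, with the groups named, or replace it with a supporting covariate-adjusted ROC analysis.

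The cost is rewording and routine analysis. The criterion becomes stricter than a test for any difference, and the minimum has to be justified beforehand. If only about 20 cancers are found, even a true AUC of 0.85 may miss the criterion in the cancer contrast, so the minimum should be chosen with the expected size of each group in view.

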4.5 Interim analysis

An interim analysis with regard to the primary endpoint will be performed after inclusion and evaluation of 250 persons. If H0 can be rejected at this stage the study will be stopped. All persons included in the study up to the decision to stop will be evaluated and considered for a secondary analysis. If H0 cannot be rejected at this stage, a re-design is possible because of the adaptive strategy.

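### The confirmatory Fisher test of p1=p2 is undefined; at a cut-off selected in the same participants, its natural reading, it exceeds a nominal 5% error rate, and on any other reading it does not address the primary endpoints

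*Protocol*

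**What the plan says.** Protocol section 3.3 sets the endpoints: "The primary endpoints are firstly the cut-off of the serum Neurotensin and IL-8 values selected by the ROC curves", together with the area under the curve. Section 3.1 says where the cut-offs come from: "Two primary analyses will be conducted to define the cut-off plasma values for Neurotensin and IL-8", one for cancer (group A v group C) and one for adenoma (group B v group C), all in this study's own participants.

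Section 4.1, the confirmatory analysis, opens with "In order to compare the low to high risk groups, the propensity score will be used". It describes a propensity model and closes that paragraph with "H0: p1=p2 is tested against the alternative H1", tested "using the exact Fisher tests". A separate paragraph then says that a ROC curve will summarise each marker's performance "for cancer and adenomas across the range of possible thresholds".

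Section 4.5 plans an interim analysis of the primary endpoint at 250 persons: "If H0 can be rejected at this stage the study will be stopped".

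The protocol does not define p1, p2, the risk groups, the significance level or the rule that picks a cut-off from the ROC curve.

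**The concern.** Neurotensin and IL-8 are continuous, while Fisher's test needs a two-by-two table. To apply it to a marker, someone must split the marker, and the only split planned for this study's participants is the ROC cut-off found in those participants. Fisher's p-value assumes that the split was fixed before the data were seen. If the threshold is chosen because it separates diseased from normal well, and the test is then run at that threshold, the p-value is too small even when the marker carries no information.

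This is separate from optimism in the reported sensitivity and specificity, and from multiplicity over markers or looks. A correction for those would leave it in place. At stake are the only analysis labelled confirmatory and the decision to stop at 250. A marker with no value for adenoma, for example, could end the study and be reported as confirmed.

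**Working it through.** **1. The plan's own figure.** Section 3.5 sizes the study for a 95% interval of total width 0.1 around AUC 0.85. With the binormal variance V = 0.0099·exp(−A²/2)·[(5A²+8) + (A²+8)/R], A = 1.414·z(0.85) = 1.4655 and R = (1−prevalence)/prevalence:

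- 30%: R = 2.333, V = 0.0781, cases = 1.96²·0.0781/0.05² = 120.0, N = 120.0/0.30 = 400.
- 20%: R = 4, V = 0.0720, cases = 110.6, N = 110.6/0.20 = 553.

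Both printed figures are reproduced. They rest on AUC precision and contain no p1, p2 or test level, so the sample-size section does not say what the Fisher test compares.

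**2. Inputs for the test.**

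- Total 500, interim 250 (sections 1.5, 4.5).
- Adenoma or cancer in 20-30% (3.5).
- Cancer in 4%, the pick-up rate in 1.8: 0.04 × 500 = 20 cancers, and 10 at the interim. Using this rate here is an assumption.
- At 20%: 100 diseased, so 80 adenomas and 400 normal. At 30%: 150 diseased, so 130 adenomas and 350 normal.
- Direction: low neurotensin and high IL-8 count as positive, from the pilot in 2.1.1. The pilot cut-offs are for cancer; the same direction is assumed for adenoma.
- Two-sided 5%: assumed, as none is stated.
- Cut-off rule: not stated. Two common ones were tried: Youden (maximum sensitivity + specificity − 1) and closest-to-corner (minimum (1−sensitivity)² + (1−specificity)²).

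**3. Simulation under no marker-disease association.** Select the cut-off, form the table, apply Fisher's exact test, and count p < 0.05. Final-analysis rows use 8,000 trials each.

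| Diseased v normal | Youden, direction fixed | Corner, direction fixed | Youden, direction from data | Corner, direction from data |
|---|---|---|---|---|
| Cancer, 20 v 400 | 17.4% | 8.3% | 31% | 16.9% |
| Cancer, 20 v 350 | 17.4% | 8.9% | 31-33% | 16.6% |
| Adenoma, 80 v 400 | 21.6% | 8.3% | 38% | 17.0% |
| Adenoma, 130 v 350 | 21.6% | 8.1% | 38-40% | 16.0% |
| All diseased, 150 v 350 | 22.3% | 8.5% | 37-39% | 14.8% |

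The last row is not a planned comparison; it shows the size effect. A repeat run of 6,000 trials gave 23.3% for 150 v 350 with Youden. At interim sizes, with direction fixed, the same run gave:

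- 10 v 175: 14.2% (Youden), 9.1% (corner);
- 10 v 188: 15.2% and 9.8%;
- 52 v 188: 19.4% and 7.8%.

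Hence about 14-23% for Youden and 8-10% for closest-to-corner.

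**4. Does selection cause it?** With the cut-off fixed beforehand (10%, 20% or 50% of null subjects positive), the exact size of Fisher's test is 2.7-4.4%. With the cut-off taken from one half and tested in the other, it is 3.6-4.1%. Both are below 5%, so the excess comes from selecting and testing in the same people.

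**5. With the interim.** Youden, direction fixed, a look at half and a final look each at 5%: 30.7% (100 v 400) and 32.2% (150 v 350). This mixes selection with an unadjusted second look.

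**The case against.** The strongest reply is that the protocol never says the Fisher test is run at the ROC cut-off. The Fisher sentence belongs to the paragraph on risk groups and propensity scores. The ROC paragraph is separate and only summarises performance over all thresholds. The same hypotheses reappear in 4.2 for adenoma frequency and other qualitative characteristics, which suggests disease proportions between groups. The risk groups could be formed by two-week referral or FOB status (3.1, 4.2), and then no cut-off is selected. This stands: the marker reading is an inference. It does not rescue section 4.1, because a comparison by referral or FOB status is not a test of the marker cut-offs or AUC named as primary endpoints.

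A reader might also infer that the definition of p1 and p2 is immaterial because either way the table is the same. That is true of marker-positivity by disease and disease by marker group. It fails if risk group means referral or FOB status.

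The simulation ignores the matching and propensity adjustment in 3.4 and 4.1. The study calls itself a pilot (section 2), would lead to a further multicentre study (5.5), and has its size set by AUC precision. These points soften the consequences. Detail may also be left to a SAP, but here the protocol itself fixes the test, the source of the cut-off and the stopping consequence.

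**Conclusion.** The point holds in conditional form. Section 4.1 fixes a confirmatory test whose quantities are undefined and which does not match the primary endpoints. If p1 and p2 are formed at the cut-off selected in the same participants, the false-positive rate per marker and comparison exceeds a nominal two-sided 5% under every rule tried: about 8-10% for closest-to-corner and about 14-23% for Youden with direction fixed by the pilot, and up to about 40% if direction is also taken from the data. On any other reading the test leaves the primary endpoints untested. In both cases section 4.5 ties early stopping to it.

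A reader might infer that a useless marker will be confirmed in some single percentage of trials, such as the Youden figure. The protocol does not support that: it states neither the selection rule nor alpha, and the lower range is equally compatible with its text. The case counts also rest on the 4% cancer rate and the 20-30% prevalence.

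**What to change.** In 4.1 and 4.5, replace the Fisher test with a test of the undichotomised marker, separately for A v C and B v C: AUC against 0.5, or the Mann-Whitney test already listed in 4.3. State alpha, and name this hypothesis as the H0 that governs stopping in 4.5. The ROC cut-offs remain as estimated endpoints. This also matches the AUC basis of the sample size in 3.5.

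If a dichotomised test is kept, define p1 and p2 and do one of two things:

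- Fix the cut-off before any sample is assayed. The pilot values in 2.1.1 (neurotensin 54.47 pg/ml, IL-8 8.83 pg/ml) were derived for cancer only, and no adenoma value is given, so they do not settle B v C.
- Take the p-value from permutations that repeat the cut-off selection each time.

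The cost is a change of wording in two sections and no new data. The downside is a less favourable nominal p-value.

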1.2 TITLE OF THE STUDY

The combined use of serum Neurotensin and IL-8 as screening markers for

colorectal cancer and adenomas. A prospective study.

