2. INTRODUCTION

Cancer research offers a better insight into regulatory mechanisms involved in cell proliferation in colorectal cancer, and might eventually guide us to new possibilities in terms of novel biomarkers that would facilitate early diagnosis.

Neurotensin (NT) mediates its effects by binding to three neurotensin receptors NTSR-1, -2, and -3: the first two are G-protein coupled receptors, whereas the third belongs to the sortilin receptor superfamily. [6-8] NT via NTSR-1 initiates a multiplicity of intracellular signaling pathways in colon cancer cells and in non-transformed NCM460 colonocytes, as well as the epidermal growth factor receptor (EGFR) and downstream mitogenactivated protein kinases (MAPK) via the metalloproteinase-dependent cleavage of pro- TGF alpha.[9] NT-mediated activation of MAPK signaling and the downstream transcription factor activator protein 1 (AP1) also occurs rapidly in human colorectal cell lines.[10] Moreover, transactivation of the IL-8 promoter is triggered by NT-mediated AP1 activation [10, 11] while NT also stimulates Ras pathway and nuclear factor kappa-light-chain-enhancer of activated B cells (NF-kB) -dependent secretion of IL-8.[6, 12] Intense transcription of the NTSR-1 gene via TCF/Lef- and nuclear β-catenindependent pathways can explain NTSR-1 overexpression in colon cancer.[13] Higher NT levels are also obtained from colon cancers compared to normal colon tissues, and in vivo evidence establishes that NT/NTSR-1 signaling is fundamental for tumor growth.[14]

Gui et al [15] found that NTSR1 expression was considerably increased in both adenomas and adenocarcinomas compared with histologically normal epithelium and in adenocarcinomas compared with adenomas.

Given that colorectal cancer is the second leading cause of cancer-related death in Europe and the third in the USA, a new non-invasive screening modality with the potential for high population compliance at a lower cost than the current screening system and with the capacity for early detection of

colorectal cancer and precursor adenomatous polyps is of paramount importance.[16, 17]

This pilot study aims to investigate whether specific pattern of serum neurotensin/NTSR1/IL-8 values can detect patients with adenomas or colorectal cancer and determine the feasibility of these agents being used as a screening tool.

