2.1 EVIDENCE

2.1.1 Serum neurotensin/IL-8 values in colorectal cancer

Serum neurotensin/IL-8 values in the diagnosis of colorectal cancer have been reported for first time in literature by our own group.[18, 19] This pilot study aimed to determine the feasibility of serum neurotensin/IL-8 values being used as a screening tool for colorectal cancer. Fifty-six patients and 15 healthy controls were assigned to seven groups according to their disease entity based on theater records and histology report. Blood samples for neurotensin and IL-8 were measured using an enzyme-linked immunosorbent assay.

There were no differences in the clinical and biochemical parameters of patients and controls. Group (p= 0.003) and age (p= 0.059: marginally significant) were independent predictors of neurotensin plasma values. Neurotensin (p= 0.004) and IL-8 (p= 0.029) differed between healthy and colorectal cancer patients. Neurotensin values differentiated the control group from all remaining groups.

The value of plasma neurotensin ≤54.47 pg/ml at enrollment selected by ROC curves demonstrated a sensitivity of 77%, specificity of 90%, and an estimate of area under ROC curve (accuracy) of 85% in predicting colorectal cancer.

At enrollment, the value of plasma IL-8 ≥8.83 pg/ml had a sensitivity of 85%, specificity 80%, and an estimate of area under ROC curve (accuracy) of 81% in predicting colorectal cancer.

Our results depicted that IL-8 should be used complementary to neurotensin due to its lower specificity. None of the colorectal cancer patients displayed a combination of high neurotensin and low IL-8 values (beyond cutoffs). Unpredictably, 3 out of 13 patients in the colorectal cancer group had neurotensin values above the cut-off value defined by the ROC curve. Notwithstanding, the IL-8 values of the same patients were high and well above the cut-off value, as our analysis anticipated for this group. Two other colorectal cancer group patients unexpectedly had low IL-8 values, but they also had low neurotensin values, as our analysis expected for this group. None of the colorectal cancer group patients displayed a combination of high neurotensin and low IL-8 values (which would be in contrast with our analysis).

Finally, one healthy control had a low neurotensin value as well as a low IL-8 value.

This pilot study[18] implicated that a blood neurotensin/IL-8 system may be used as a screening tool for colorectal cancer.

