The addition of NTSR1 was of paramount importance. Neurotensin and its receptors stimulate cancer cell growth[6], mainly through binding to NTSR1, which is overexpressed in many cancer cell lines.[20]

According to our model individuals with low Neurotensin values (according to the defined cutoff) should be suspected for bearing colorectal cancer needing further assessment with colonoscopy. In this patient population having low

Neurotensin plasma values there is no need to search for IL-8 values. As a second step, individuals with high Neurotensin values and high IL-8 values should also undergo colonoscopy. Accordingly, IL-8 values should be considered as complementary to Neurotensin measurement and not as a standalone screening marker.

The diagnostic performance of a blood neurotensin/IL-8 system for colorectal cancer proved to be satisfactory. The American Cancer Society, for instance, conducted a systematic review of the literature assessing PSA performance. [21] A pooled analysis showed the estimated sensitivity of a PSA cutoff of 4.0 ng/mL as 21% in detecting prostate cancer and 51% in detecting high-grade cancers (Gleason score \geq 8) while the corresponding sensitivity using a cutoff of 3.0 g/mL was higher: 32% and 68%, respectively.

We consider the fact that not a single colorectal cancer patient in our study displayed a combination of high neurotensin and low IL-8 plasma values to be the most important finding.

Martin et al [22] conducted a thorough analysis to explore the functional significance of SORT1/NTSR1 heterodimers in HT29 cells. SORT1 shifted the neurotensin dose-response curve to the right whilst increasing maximal stimulation for ERK phosphorylation two-fold. The authors proposed that interaction between NTS1 and SORT1 produced a new means of cell activation that could prove essential for the growth effect of neurotensin. Whether this mechanism can justify the high neurotensin values (above the cut-off value) in three of our colorectal cancer group patients is uncertain. Low IL-8 values of two colorectal cancer patients were possibly due to the use of statins. The mechanism of anti-inflammatory activity of statins became

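### The primary analysis does not include the two-step neurotensin/IL-8 rule that the title and aim are about, and the single-marker ROC curves cannot supply its accuracy

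*Protocol*

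**What the plan says.** The question is about the two markers together. The Protocol title (1.2) begins "The combined use of serum Neurotensin and IL-8 as screening markers for", and the Introduction (section 2) states: "This pilot study aims to investigate whether specific pattern of serum neurotensin/NTSR1/IL-8 values can detect patients with adenomas or colorectal cancer".

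Section 2.1.1 turns this into a rule. Step 1: "individuals with low Neurotensin values (according to the defined cutoff) should be suspected for bearing colorectal cancer needing further assessment with colonoscopy". Step 2: "As a second step, individuals with high Neurotensin values and high IL-8 values should also undergo colonoscopy". It adds that "IL-8 values should be considered as complementary to Neurotensin measurement and not as a standalone screening marker". It names as its most important pilot result that no cancer patient combined high neurotensin with low IL-8, which is a statement about the joint rule.

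The primary analysis is set in three places:

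- Section 3.1 plans two primary analyses, cancer versus normal (A versus C) and adenoma versus normal (B versus C), each to define cut-offs for the two markers.
- Section 3.3 makes the ROC-selected cut-offs and the AUC the primary endpoints.
- Section 4.1 uses ROC analysis to "summarize the performance of the two-class classifiers (for Neurotensin and IL-8) for cancer and adenomas across the range of possible thresholds".

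The neurotensin/IL-8 system is named only as a secondary analysis in 3.1 and an exploratory one in 4.2. Both compare it with 2-week referral/FOB, and 4.2 does so by propensity scoring in logistic regression. Neither mentions the two-step rule.

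**The concern.** A ROC curve needs one score per person. Sections 3.1, 3.3 and 4.1 give no function that combines the markers, so the natural reading is a neurotensin curve and an IL-8 curve. The rule in 2.1.1 is positive when either marker is abnormal. Compared with each marker at the same cut-offs, such a rule cannot have lower sensitivity or higher specificity. How far each moves depends on the joint distribution of the markers, which separate curves do not show.

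Followed as written, the study could report two AUCs and two cut-offs and still not say how well the proposed test works. Specificity is the figure most at stake, because section 1.8 motivates the study partly by the number of unnecessary colonoscopies.

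A second, smaller issue is that sensitivity and specificity quoted at cut-offs chosen on the same data are optimistic, most of all where cases are few.

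**Working it through.** **Planning figure.** Section 3.5 gives 400 participants (30% prevalence) to 553 (20%) for a 95% CI of total width 0.1 around AUC 0.85. The Obuchowski binormal variance reproduces this:

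- V = 0.0099·exp(−a²/2)·[(5a²+8) + (a²+8)/k], with a = 1.414·z(0.85) = 1.4655 and k = (1−prevalence)/prevalence.
- Cases = 1.96²·V/0.05², and N = cases/prevalence.
- At 20%: k = 4, V = 0.0720, cases = 110.6, N = 552.9.
- At 30%: k = 2.333, V = 0.0781, cases = 120.0, N = 400.0.

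The arithmetic is right. The AUC of 0.85 is the pilot value for neurotensin alone (IL-8 was 0.81), so the planning figure is also a single-marker one.

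**Pilot inputs (2.1.1), cancer only.**

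- Neurotensin ≤54.47 pg/ml: sensitivity 77%, specificity 90%.
- IL-8 ≥8.83 pg/ml: sensitivity 85%, specificity 80%.
- Of 13 cancers, 3 had neurotensin above its cut-off, all with high IL-8. Two had low IL-8, both with low neurotensin.

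**Sensitivity (exact 95% CI).**

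| Test | Detected | Sensitivity |
|---|---|---|
| Neurotensin | 13 − 3 = 10/13 | 77% (46-95%) |
| IL-8 | 13 − 2 = 11/13 | 85% (55-98%) |
| Two-step rule | 13/13 | 100% (75-100%) |

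The lower limit for 13/13 is 0.025^(1/13) = 0.753.

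**Specificity of the rule.** A control is negative only if negative on both markers.

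- Lower bound: 0.90 + 0.80 − 1 = 0.70.
- Upper bound from the margins alone: min(0.90, 0.80) = 0.80.
- Section 2.1.1 reports one healthy control with low neurotensin and low IL-8. That control is IL-8 negative but positive on the rule, so 80% cannot be reached.
- Result: at least 70% and below 80%.

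These bounds use the percentages as reported. With 15 controls, 90% is not an attainable fraction (13/15 = 87%, 14/15 = 93%), so the rule's specificity can only be bounded.

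**False positives.** Assume 375 group C participants, which is 500 × (1 − 0.25), the middle of the protocol's 20-30% prevalence range, and assume that the pilot specificities carry over.

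- Rule: 375 × 0.20 = 75 to 375 × 0.30 = 112.5, so roughly 75-113.
- Neurotensin alone at 90%: 375 × 0.10 = 37.5, about 38.

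**Optimism from choosing cut-offs on the study data.** Simulation of one marker: equal-variance binormal model, AUC 0.85, 375 normals, Youden cut-off, 4,000 runs. The protocol names no criterion, so Youden is an assumption. So are 20 cancers (500 × the 4% pick-up rate in 1.8) and 100-125 adenomas (20-25% of 500).

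| Cases | Apparent sensitivity | True sensitivity | Optimism |
|---|---|---|---|
| 20 cancers | 82% | 74% | about 9 points |
| 100-125 adenomas | 79% | 76% | about 3 points |

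The 9 points come from unrounded values (0.822 − 0.735). Specificity shifts by less than 1 point.

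**The case against.** Five arguments can be made for the plan.

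1. **Separate curves are an inference.** The protocol does not use that word, section 3.5 speaks of one new test, and the SAP, which is not shown, could supply a combining formula. This stands as a caution on wording. But the protocol itself fixes the primary endpoints, and an SAP would normally elaborate them, not replace them.

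2. **The combination is not ignored altogether.** Sections 3.1 and 4.2 do assess the two-marker system. That is correct, so the point concerns the primary analysis only. Those sections do not evaluate the rule of 2.1.1 either.

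3. **An IL-8 ROC curve is not an error.** A reader might infer that it contradicts the statement in 2.1.1 that IL-8 is not for use alone. It does not. That statement concerns screening use, and step 2 of the rule needs an IL-8 cut-off, which the curve can supply.

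4. **Defining new cut-offs is legitimate.** A reader might infer that the pilot cut-offs ought to be the fixed primary thresholds. The documents do not support that. Section 3.1 states that the aim is to define cut-offs, and the pilot values are for cancer only, so they cannot serve B versus C. They are described as plasma values, while this protocol mixes plasma and serum. The pilot kit is not stated.

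5. **The size can be overstated.** Counting every participant without cancer as a potential false positive would include adenoma patients, who are themselves a detection target, so group C is the right denominator. The 9-point optimism applies to the cancer comparison with few cases. A single-marker AUC carries no optimism from cut-off selection.

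Both markers are to be measured in participants, so the rule can be computed later without a design change. That limits the harm, but it does not make the rule's accuracy a pre-specified primary result.

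**Conclusion.** The point holds for the primary analysis. Sections 3.1, 3.3 and 4.1 do not name the two-step rule, a combined score, or their sensitivity and specificity, although the title, the aim and section 2.1.1 make the combination the question. On pilot figures the rule differs materially from neurotensin alone: sensitivity 100% against 77%, and specificity from 70% to below 80% against 90%.

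The sensitivity comparison rests on 13 cancers. The false-positive range rests on 375 group C participants and on pilot specificities carrying over. The optimism figures rest on the Youden criterion, the binormal model and the assumed case numbers.

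The data remain usable and the sample-size arithmetic is sound. The defect lies in what is declared primary. It should be corrected before the analysis.

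**What to change.** In sections 3.3 and 4.1:

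- Add as a primary result the sensitivity and specificity, with exact 95% CIs, of the two-step rule for A versus C and for B versus C.
- Report alongside it the AUC of a two-marker model against neurotensin alone.
- Keep the single-marker ROC curves as the step that sets the cut-offs.
- Where cut-offs are derived on the study data, name the selection criterion and report bootstrap or cross-validated optimism-corrected sensitivity and specificity.
- For cancer only, report the rule at the fixed pilot cut-offs (54.47 and 8.83 pg/ml) as a supporting analysis, with a caveat on assay and sample type.

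The cost is protocol wording and a little more analysis. No further participants, samples or assays are needed. The reported specificity will probably look less favourable than the single-marker 90%.
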